Prostate MRI is essential for cancer staging within the gland, but limited in detection of nodal metastases. While prostate MRI is valuable for the staging of the known cancer, its sensitivity and specificity for the detection of pelvic lymph node metastases is limited by RECIST 1.1 criteria and nodal morphology. Molecular imaging has great potential to supplement MRI and increase diagnostic accuracy, and simultaneous PET/MRI can provide both dedicated pelvic PET and MRI imaging for regional staging as well as whole body staging in a single imaging session.

PSMA PET ligands show great promise for detection of both intraprostatic and extraprostatic disease. Prostate specific membrane antigen (PSMA) is a transmembrane cellular receptor that is overexpressed in prostate cancer cells. Recently, small molecules have been developed that bind to the extracellular component of the transmembrane PSMA receptor. These agents have been tagged with both ^{18}F and ^{68}Ga for imaging and ^{90}Y and ^{177}Lu for therapeutic purposes. Restaging accuracy of fluciclovine and PSMA-PET/CT are superior to choline compounds, particularly at low PSA levels, and a single 10 patient case series suggests superiority of PSMA PET over fluciclovine.[4, 5] A limitation of PSMA ligands is that approximately 10% of prostate carcinoma and nodal metastases are PSMA negative.¹⁻⁴

PET imaging has been shown to alter radiation treatment planning in patients with recurrent prostate cancer. The concept of PET guided radiation therapy is well-established and utilizes standardized uptake values (SUV) within lesions to automatically segment target volumes.[6-8] The technique has been evaluated previously in recurrent prostate cancer with use of $[^{11}\text{C}]$ choline and $[^{18}\text{F}]$ fluorocholine PET/CT with increases in detected gross tumor volume.[9, 10] PSMA-PET/CT has been demonstrated to be superior to $[^{11}\text{C}]$ choline PET/CT in recurrent prostate cancer in both sensitivity and specificity and has been shown to alter radiation therapy management in a substantial fraction of patients.[11-14] Therefore, we expect that PSMA-PET/MRI will be valuable in the initial staging and radiation treatment planning in patients with oligometastatic prostate cancer and that target lesion segmentation is feasible utilizing SUV thresholding.

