6.2 Study Objectives

Specific Aim #1: Determine the concordance of imaging findings for PSMA-PET/MRI and MRI of the pelvis and prostate gland.

Hypothesis #1: PSMA-PET/MRI will identify more regional lymph node metastases than MRI alone.

There have been numerous prior studies demonstrating the value of MRI for the locoregional staging for PCa. We expect the simultaneous acquisition of MRI and PSMA PET data to provide valuable preoperative staging information, with PSMA PET detecting metastatic disease in subcentimeter pelvic lymph nodes not identified with MRI alone. Additionally, PSMA-PET/MRI provides whole body staging in regions not evaluated by pelvic MRI and may detect additional distant metastases.

Specific Aim #2: Establish feasibility and assess acute toxicity of PSMA-PET/MRI directed pelvic radiotherapy.

Hypothesis #2: PSMA-PET/MRI directed radiation therapy will be feasible in the vast majority of patients (>90%) and can be safely administered without increased acute radiation toxicities.

The primary goal of Specific Aim 2 is to provide preliminary information to confirm the feasibility of radiation dose escalation to the suspicious LNs identified on PSMA-PET/MRI. If results from this trial are supportive, this will lead to a larger clinical trial evaluating efficacy and disease outcomes between patients who have undergone PSMA-PET/MRI directed radiotherapy versus standard-of-care pelvic radiotherapy.

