6.5.5 Study Variables and Key Endpoints

For specific aim 1, we will assess the concordance between prostate MRI and PSMA-PET/MRI for the detection of seminal vesicle invasion and pelvic metastatic disease. The total number of pelvic nodal metastases detected on MRI and PSMA-PET/MRI will be compared. The confidence in detection of seminal vesicle invasion on a 0-3 Likert scale will also be compared between MRI and PSMA-PET/MRI. The primary endpoint for specific aim 1 number of patients who demonstrate pelvic LN metastases on PSMA-PET/MRI that were not detected on conventional anatomic imaging. We expect at least 25% of patients to demonstrate pelvic LN metastases that were not detected on conventional anatomic imaging.

For specific aim 2, study participants who remain eligible for pelvic radiation therapy (e.g. no distant metastases) will be subdivided into two cohorts: those without suspicious extraprostatic activity on PSMA-PET/MRI and those whose PSMA-PET/MRI demonstrates suspected seminal vesicle invasion and/or pelvic nodal metastatic disease. Those without suspicious extraprostatic uptake will undergo standard-of-care radiation therapy. Patients with positive PSMA-PET/MRI scans will undergo radiation treatment planning with a boost given to the suspicious lesions. The primary endpoint of specific aim 2 is to assess the number of patients with positive PSMA-PET/MRI scans where the radiation boost is feasible. We expect that the radiation treatment planning will be feasible in at least 90% of patients with positive PSMA-PET/MRI scans. A secondary endpoint is to compare the frequency of acute radiation toxicities between the cohorts. We expect that less than 15% of patients who undergo PSMA-PET/MRI directed LN radiotherapy boost will experience CTCAE v5.0 grade 3+ genitourinary or gastrointestinal toxicities and that no patient will experience a grade 5 genitourinary or gastrointestinal toxicity. All grade 3 toxicities will be reviewed by the radiation oncology sub-investigator. If any grade 4 or 5 events occur, the cases will be reviewed among members of the study team and the study will potentially be paused/terminated if there is concern that deviation from standard of care radiation therapy has caused undue harm to the patient.

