6.6.3 Analysis

Demographic and clinical characteristics of all the enrolled patients will be summarized using descriptive and graphical statistics. Mean and standard deviation will be provided for continuous variable and counts and percentage will be for categorical variables. To ensure the quality of imaging data, imaging data from three readers will be assessed first using Kappa statistics (K) for inter-rater agreement.

For the primary analysis in Aim 1, the number of patients who are identified with lymph node metastases (positive nodal) will be counted, and percentage and 95% exact confidence interval will be calculated using the Clopper-Pearson method for PSMA-PET/MRI and MRI respectively.

Concordance and agreement between two methods will be evaluated using Cohen's kappa statistic, κ . For the primary analysis in Aim 2, SUV thresholding, CTV, and other imaging parameters between PSMA-PET/MRI and MRI will be determined using the Bland-Altman plot analysis in addition to descriptive analysis. Safety analysis of acute radiation toxicities related AE/SAE in Aim 2 will be descriptive, such as frequency and percentage will be reported. We will also report the frequency of patients with any grade 3 GI or GU toxicity, and any grade 4-5 toxicity. All statistical analysis will be carried out using the Statistical Analysis Software SAS v 9.4.

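### The analysis labelled primary for Aim 2 (Bland-Altman on imaging parameters) does not analyse the Aim 2 primary endpoint, which is a count of scan-positive patients with a feasible boost

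*Combined protocol and SAP*

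**What the plan says.** Section 6.5.5 states that the Aim 2 primary endpoint is to "assess the number of patients with positive PSMA-PET/MRI scans where the radiation boost is feasible". The accompanying expectation is that treatment planning will be "feasible in at least 90% of patients with positive PSMA-PET/MRI scans". The setting for the count is given just before: "study participants who remain eligible for pelvic radiation therapy (e.g. no distant metastases) will be subdivided into two cohorts", one without suspicious extraprostatic activity and one whose scan "demonstrates suspected seminal vesicle invasion and/or pelvic nodal metastatic disease".

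Section 6.6.3 then describes the primary analysis for Aim 2 in one sentence: "SUV thresholding, CTV, and other imaging parameters between PSMA-PET/MRI and MRI will be determined using the Bland-Altman plot analysis", with descriptive analysis added. Its only other Aim 2 content is a descriptive report of acute toxicity.

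For Aim 1 the same section says that the "percentage and 95% exact confidence interval will be calculated using the Clopper-Pearson method" for each imaging method.

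Section 6.2 puts the Aim 2 goal as preliminary information to "confirm the feasibility of radiation dose escalation to the suspicious LNs identified on PSMA-PET/MRI", states the hypothesis as feasibility above 90%, and says supportive results will lead to a larger trial.

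**The concern.** The endpoint is binary for each patient: the boost is feasible or it is not. The analysis called primary compares imaging quantities between two methods. A statistician following 6.6.3 literally would produce Bland-Altman plots under the Aim 2 primary heading and would have no instruction to tabulate feasibility, no stated denominator and no interval.

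The feasibility result is what Section 6.2 offers as support for a larger trial. Readers of the pilot will need the proportion and its uncertainty. With so few patients, a bare statement that every plan was feasible would look much firmer than it is.

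**Working it through.** **1. Endpoint and analysis side by side**

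| | Section 6.5.5 (endpoint) | Section 6.6.3 (analysis labelled primary) |
|---|---|---|
| Unit | Scan-positive patient | Imaging measurement |
| Variable | Boost feasible, yes or no | SUV thresholding, CTV, other imaging parameters |
| Result | Count and share, read against 90% | Agreement between PSMA-PET/MRI and MRI |

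**2. What Bland-Altman can deliver.** It takes paired values a and b of the same quantity, forms d = a − b, and reports the mean of d with limits of agreement (mean ± a fixed multiple of the SD of d). No step produces a count of patients. The reading kindest to the plan is that the parameters are volumes derived from SUV thresholds, since Section 6.1 expects that "target lesion segmentation is feasible utilizing SUV thresholding". Even so, a volume difference bears on one component of feasibility and does not say in how many patients a boost could be planned. Part of the list also lacks a pair: Section 6.4.6.3 takes SUVs from PET, while MRI is read qualitatively.

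**3. Whether another sentence in 6.6.3 fills the gap.** The sentence on counts and percentages follows one limited to demographic and clinical characteristics. The mention of descriptive analysis sits in the imaging-parameter sentence. Kappa is used for reader agreement and for concordance of the two methods, and Clopper-Pearson is given for Aim 1. Feasibility is not named.

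**4. What the missing analysis would show.** There is no plan figure to reproduce, because Section 6.6.1 says no power or sample size calculation was done. Inputs:
- Total enrolment is 10 (Sections 6.0 and 6.3.1), so m, the number of eligible scan-positive patients, is at most 10.
- The documents do not give m. The range 4 to 10 is an assumption.
- The method is the exact 95% Clopper-Pearson interval, as for Aim 1.

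For x feasible out of m, the lower limit is the 0.025 quantile of Beta(x, m − x + 1) and the upper limit is the 0.975 quantile of Beta(x + 1, m − x). When x = m, the lower limit reduces to 0.025^(1/m) and the upper limit is 100%.

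| m | All feasible: 95% CI | One infeasible: share (95% CI) |
|---|---|---|
| 4 | 39.8% to 100% | 3/4 = 75.0% (19.4% to 99.4%) |
| 6 | 54.1% to 100% | 5/6 = 83.3% (35.9% to 99.6%) |
| 8 | 63.1% to 100% | 7/8 = 87.5% (47.3% to 99.7%) |
| 10 | 69.2% to 100% | 9/10 = 90.0% (55.5% to 99.7%) |

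For the lower limit to exceed 90% with no failures, 0.025^(1/m) must exceed 0.90. At m = 35 it is 89.997% and at m = 36 it is 90.3%, so 36/36 would be needed.

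**5. The two versions of the 90% mark.** Section 6.2 says above 90%; Section 6.5.5 says at least 90%. With m = 10 and one failure, 9/10 = 90.0% meets the second and not the first. With m of 9 or fewer, one failure gives at most 8/9 = 88.9% and misses both, so the wordings differ in practice only at 9/10.

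**6. Why the denominator should be written down.** Section 6.6.2 defines the analysed population only as men meeting the inclusion criteria. As an illustration, one planning failure among 8 scan-positive patients gives 7/8 = 87.5% (47.3% to 99.7%) if kept in m, and 7/7 = 100% (59.0% to 100%) if left out. No passage proposes leaving failures out; the text is silent.

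**The case against.** The strongest defence is that this is a 10-patient pilot with no power calculation, that the endpoint is worded as a number of patients, and that a plain count answers it. Section 6.6.3 mentions descriptive analysis in the Aim 2 sentence and counts and percentages for categorical variables, so x out of m would very likely be reported, and any reader could then compute the interval. Toxicity is also planned without intervals, and no interval from so few patients could support 90%.

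Much of this stands, and it limits the seriousness. No patient, data item or comparison is lost, and the missing interval is the weaker half of the point. The defence does not remove the contradiction. Those descriptive phrases attach to imaging parameters and to baseline characteristics, and a different analysis still carries the primary label. Pilot status explains the absence of a power calculation, not a primary endpoint without an analysis. Aim 1 of the same pilot has an exact interval.

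Two stronger readings are tempting and are not supported. First, a reader might infer that the trial is set to fail a 90% test. No passage ties a decision to 90%; it is an expectation. Second, a reader might infer that men positive only for seminal vesicle invasion have no boost volume and so cannot count as feasible. Section 6.5.2 puts the whole seminal vesicles in the prostate volume when gross invasion is identified, and Section 6.5.3 describes an integrated boost to the prostate and proximal seminal vesicles. What remains is a wording conflict: Section 6.5.5 refers to boosting suspicious lesions, the goal in Section 6.2 and the PSMA-defined boost volume in Section 6.5.2 concern nodes, and the prostate and seminal vesicle volume is described as standard of care.

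**Conclusion.** The point holds. The endpoint in Section 6.5.5 and the analysis labelled primary in Section 6.6.3 answer different questions, and the feasibility count has neither a named analysis nor an interval. This is a contradiction in the text and does not depend on any assumed number. It should be fixed, but it does not threaten the trial: the count can be recovered from data the study will hold.

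The size of the uncertainty left unreported is large. The best possible result, 10/10, has a lower limit of 69.2%, and smaller m gives lower limits still. These figures assume m between 4 and 10 and the interval method already chosen for Aim 1. They show precision only; adding the interval would not enable the study to confirm 90%.

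**What to change.** In Section 6.6.3:

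- Make the Aim 2 primary analysis the feasible count x over m, with percentage and exact Clopper-Pearson 95% interval.
- Define m as all patients with a positive PSMA-PET/MRI who remain eligible for pelvic radiotherapy, following Section 6.5.5, and state that planning failures stay in m.
- Relabel Bland-Altman as secondary or exploratory and limit it to quantities measured by both methods.

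The sponsor should also reconcile these passages:

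- Section 6.5.5 speaks both of the boost being feasible and of treatment planning being feasible. State which is the endpoint.
- State whether the plan-acceptability criteria in Table 2 (Section 6.5.3) define feasible. The text does not link them, and the table's footnote sets no minimum acceptable coverage for the nodal boost planning volume.
- Choose one wording of the 90% mark, since Sections 6.2 and 6.5.5 differ at 9/10.
- Reconcile Sections 6.2, 6.5.2, 6.5.3 and 6.5.5 on how a patient positive only for seminal vesicle invasion is counted.

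No dose or clinical rule is proposed here. The cost is a protocol amendment approved by the IRB and FDA (Section 6.7.3), with no new patients or data. The downside is that the published interval will be wide.

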6.7 Pre-Study Documentation

This study will be conducted in accordance with the ethical principles that have their origin in the Declaration of Helsinki as stated in 21 CFR §312.120(c)(4); consistent with GCP and all applicable regulatory requirements.

Before initiating this trial, the Investigator will have written and dated approval from the Institutional Review Board for the protocol, written informed consent form, subject recruitment materials, and any other written information to be provided to subjects before any protocol related procedures are performed on any subjects.

The clinical investigation will not begin until either FDA has determined that the study under the Investigational Drug Application (IND) is allowed to proceed or the Investigator has received a letter from FDA stating that the study is exempt from IND requirements.

6.7.1 Institutional Review Board Approval

The protocol, the proposed informed consent form, and all forms of participant information related to the study (e.g. advertisements used to recruit participants) will be reviewed and approved by the UAB IRB. Prior to obtaining IRB approval, the protocol must be approved by the UAB Comprehensive Cancer Center Protocol Review Committee (PRC). The initial protocol and all protocol amendments must be approved by the IRB prior to implementation.

6.7.2 Informed Consent

All participants must be provided a consent form describing the study with sufficient information for each participant to make an informed decision regarding their participation. Participants must sign the IRB-approved informed consent form prior to participation in any study specific procedure. The

participant must receive a copy of the signed and dated consent document. The original signed copy of the consent document must be retained in the medical record or research file.

6.7.3 Changes in the Protocol

Once the protocol has been approved by the UAB IRB and FDA, any changes to the protocol must be documented in the form of an amendment, submitted to and approved by both IRB and FDA.

If it becomes necessary to alter the protocol to eliminate an immediate hazard to patients, an amendment may be implemented prior to IRB approval. In this circumstance, however, the Investigator must then notify the IRB in writing within five (5) working days after implementation.

6.8 Adverse Event Reporting

As with many IV administered agents, [⁶⁸Ga]PSMA-11 could cause an allergic reaction that could potentially pose a threat to life (anaphylaxis). This has not been observed in limited human exposure to date. Reasonable precautions should be taken, consistent with normal radiologic and clinical facility practice. The patient should be monitored until the PET procedure is completed, and trained personnel and emergency equipment should be available per facility standards.

Qualifying Adverse Events (AEs), including Serious Adverse Events (SAEs), as defined herein, will be reported via the FDA Adverse Event Expedited Reporting System (AERS). For the [⁶⁸Ga]PSMA IND we will report adverse events based on the FDA final rule for IND safety reporting requirements under 21 CFR part 312 published on September 29, 2010 and implemented on March 28, 2011. This investigational study is not a BA or BE study so 21 CFR part 320 is not applicable. Adverse events will also be reported to the UAB IRB according to their requirements.

6.8.1 General Definitions (from 21 CFR 312.32 (a))

Adverse Event (AE): An Adverse Event is an untoward medical occurrence associated with the use of the drug in humans, whether or not considered drug related. For this study, the drug is [⁶⁸Ga]PSMA and adverse events would include any events experienced by a study participant during the Adverse Event reporting period defined in Table 1 whether or not it was considered to be related to the [⁶⁸Ga]PSMA. At the conclusion of the imaging study, the imaging technologist will observe the patient and also inquire if they are back to their usual state of health. If a negative answer is received, then the physician will be called to investigate this report as a possible adverse reaction.

Adverse Reaction: An Adverse Reaction is any adverse event caused by a drug. In this study, the drug is [⁶⁸Ga]PSMA.

Suspected adverse reaction means any adverse event for which there is a reasonable possibility that the IND drug caused the adverse event. For the purposes of IND safety reporting, “reasonable possibility” means there is evidence to suggest a causal relationship between the drug and the adverse event. A suspected adverse reaction implies a lesser degree of certainty about causality than adverse reaction, which means any adverse event caused by a drug.

An adverse event or suspected adverse reaction is considered “unexpected” if it is not listed in the investigator brochure or is not listed at the specificity or severity that has been observed; or, if an investigator brochure is not required or available, is not consistent with the risk information described in the general investigational plan or elsewhere in the current application.

An adverse event or suspected adverse reaction is considered “serious” if, in the view of either the investigator or sponsor, it results in any of the following outcomes: Death, a life-threatening adverse event, inpatient hospitalization or prolongation of existing hospitalization, a persistent or significant incapacity or substantial disruption of the ability to conduct normal life functions, or a congenital anomaly/birth defect. Important medical events that may not result in death, be life threatening, or require hospitalization may be considered serious when, based upon appropriate medical judgment, they may jeopardize the patient or subject and may require medical or surgical intervention to prevent one of the outcomes listed in this definition. Examples of such medical events include: allergic bronchospasm requiring intensive treatment in an emergency room or at home, blood dyscrasias or convulsions that do not result in inpatient hospitalization, or the development of drug dependency or drug abuse.

An adverse event or suspected adverse reaction is considered “life-threatening” if, in the view of either the investigator or sponsor, its occurrence places the patient or subject at immediate risk of death. It does not include an adverse event or suspected adverse reaction that, had it occurred in a more severe form, might have caused death.

Investigational Agent: An investigational agent is any agent held under an Investigational New Drug (IND) application. For purposes of this study, [⁶⁸Ga]PSMA is the investigational agent.

6.8.2 AE Reporting Requirements

The investigators on this protocol will report any suspected adverse events that occur after [⁶⁸Ga]PSMA administration and within the specified follow-up period to [name] and they will work together to determine whether there was an adverse event or adverse reaction and the severity of the adverse event or reaction.

All AEs will be followed by the investigators until resolution, stabilization, scientifically and clinically satisfactory explanation as to attribution and etiology is achieved, or until subject is lost to follow up.

